3. STUDY PATIENT POPULATION AND DISCONTINUATION

3.1. Inclusion Criteria

Patients must meet the following criteria in order to be included in the research study:

1. Signed and dated written informed consent prior to any study-specific procedures.
2. Female or male patients age ≥ 18 years at the time of providing voluntary written informed consent.
3. Histologically- or cytologically-confirmed locally advanced or metastatic solid tumor with documented recurrence or disease progression from standard anticancer therapy in the advanced/metastatic setting.
4. Eastern Cooperative Oncology Group (ECOG) Performance Status score of 0 or 1 ([Appendix A](#)).
5. Minimum life expectancy of ≥ 3 months.
6. Ability to swallow BDTX-189 tablets.
7. All toxicities from prior therapy (except alopecia, Grade 2 neuropathy, or Grade 2 hypothyroidism) must have resolved to \leq Grade 1 according to the National Cancer Institute (NCI) Common Terminology Criteria for Adverse Events ([CTCAE Version 5.0](#)) prior to baseline. Pneumonitis due to prior therapy or radiation must be totally resolved. Patients with Grade 2 neuropathy, Grade 2 hypothyroidism, or other toxicities that are asymptomatic or adequately managed with stable medication may be eligible with approval by the Sponsor.
8. For women of child-bearing potential (WOCBP), documentation of negative serum pregnancy test (beta-human chorionic gonadotropin [β -hCG]) within 7 days prior to baseline ([Appendix C](#)).
 - **Note:** WOCBP is defined as fertile, following menarche and until becoming post-menopausal (no menses for 12 months without an alternative medical cause) unless permanently sterile (hysterectomy, bilateral salpingectomy, or bilateral oophorectomy).
9. For WOCBP and male patients whose sexual partners are WOCBP, agreement to use a highly effective method of contraception during the study and for at least 90 days after the last dose of study treatment. Male patients must also refrain from donating sperm during their participation in the study ([Appendix C](#)).
 - **Note:** Highly effective birth control includes: 1) oral, implantable, or injectable combined hormonal (estrogen and progesterone containing) or progesterone only contraceptive associated with inhibition of ovulation; 2) intrauterine device; 3) intrauterine hormone-releasing system; or 4) bilateral tubal occlusion, vasectomized partner or sexual abstinence.

Part A Only

10. No standard therapy available according to the Investigator.

11. **For the dose-escalation portion**, patients with solid tumors with alterations that may be associated with antitumor activity based on preclinical data for BDTX-189 such as:

- a. [REDACTED] or [REDACTED] mutation(s)
- b. [REDACTED] or [REDACTED] mutation
- c. [REDACTED] amplified or overexpressing tumor
- d. [REDACTED] mutation

Mutations must have been determined by a validated NGS test routinely used by each institution using tissue and/or plasma and performed in a Clinical Laboratory Improvement Amendments (CLIA)-certified or equivalent laboratory. A list of eligible validated oncogenic mutations from 1 of the 7 MTCs is provided in [Appendix I](#).

Part A Safety Expansion Only

12. Patients with one of the following mutations and tumor pairs:

- a. [REDACTED] mutation in patients with NSCLC, breast cancer, biliary tract cancer, or cervical cancer
- b. [REDACTED] or [REDACTED] mutation in patients with NSCLC
- c. [REDACTED] amplified or overexpressing tumor from the following cancer types: breast, gastric, gastroesophageal, colorectal, endometrial, biliary tract, cancer of unknown primary (CUP), and NSCLC

Mutations must have been determined by a validated NGS test routinely used by each institution using tissue and/or plasma and performed in a CLIA-certified or equivalent laboratory. A list of eligible validated oncogenic mutations from 1 of the 7 MTCs are provided in [Appendix I](#).

Note: The Sponsor reserves the right to prioritize tumor/genomic alteration pairs and to cap enrollment for any of these based on the Sponsor's portfolio decision-making process.

13. Mandatory archival tumor tissue or willing to undergo pretreatment biopsy if no archival tissue available (Section [5.7.1](#)).

14. Measurable disease according to RECIST version 1.1 ([Appendix B](#)).

Part B Only

15. Patients with locally advanced or metastatic:

- a. NSCLC who have received at least one prior platinum-containing regimen (with or without an anti-PD-[L]1 antibody) and no more than 2 prior regimens for advanced NSCLC. Patients with no prior therapy who refuse standard therapy may also be eligible following discussion and approval by the Sponsor's Medical Monitor.
- b. Solid tumor other than NSCLC who have received at least one and no more than 3 prior regimens for advanced cancer.

16. Patients with solid tumor(s) harboring an:

- a. [REDACTED] mutation.
- b. [REDACTED] mutation or [REDACTED] mutation.

Mutations must have been determined by a validated NGS test routinely used by each institution using tissue and/or plasma and performed in a CLIA-certified or equivalent laboratory. A list of eligible validated oncogenic mutations from 1 of the 7 MTCs is provided in [Appendix I](#).

Eligible patients will be assigned to one of the 5 following cohorts:

Cohort 1: NSCLC with an [REDACTED] mutation from MTC-A.

Cohort 2: NSCLC with an [REDACTED] mutation from MTC-B or point mutation from MTC-C.

Cohort 3: Breast cancer with an [REDACTED] mutation from MTC-B, MTC-C, MTC-D, MTC-E, or MTC-F.

Cohort 4: NSCLC, biliary tract cancer, or cervical cancer with an [REDACTED] mutation from MTC-D.

Cohort 5: Any solid tumor type with any allosteric *ErbB* mutation from any of the 7 MTCs (MTC-A to MTC-G), excluding patients who are otherwise eligible for Cohorts 1-4.

Note: The Sponsor reserves the right to prioritize Cohorts (ie, tumor/mutation pairs) and to cap enrollment for any Cohort based on the Sponsor's portfolio decision-making process.

17. Measurable disease according to RECIST version 1.1 ([Appendix B](#)).

18. Mandatory archival tumor tissue or willing to undergo pretreatment biopsy if no archival tissue available (Section [5.7.1](#)).

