Appendix C Guidelines for Women of Childbearing Potential and Fertile Male Patients

Acceptable Contraception Methods:

Women of childbearing potential, defined as all women physiologically capable of becoming pregnant, must use highly effective contraception during the study and for at least 90 days after stopping treatment.

Highly effective contraception is defined as either:

True Abstinence	When this is in line with the preferred and usual lifestyle of the patient. Periodic abstinence (e.g., calendar, ovulation, symptothermal, post-ovulation methods) and withdrawal are not acceptable methods of contraception.
Sterilization	When a woman of childbearing potential has had surgical bilateral oophorectomy (with or without hysterectomy) or tubal ligation at least six weeks prior to study entry. In case of oophorectomy alone, only when the reproductive status of the woman has been confirmed by follow-up hormone level assessment.
Male Partner Sterilization	When there is appropriate post-vasectomy documentation of the absence of sperm in the ejaculate.

Use of the following:

Placement of an intrauterine device (IUD) or intrauterine system (IUS) or established use of oral, injected or implanted hormonal methods of contraception, bilateral tubal occlusion, vasectomized partner.

Fertile male patients, defined as all males physiologically capable of conceiving offspring, with female partners of childbearing potential must use condoms plus a spermicidal agent during the study treatment period and for at least 90 days after the last dose of study drug, and should not father a child during this period.

Male patients must also refrain from donating sperm during their participation in the study.

Unacceptable Contraception Methods for women of childbearing potential include:

- IUD progesterone T.
- Female condom.
- Natural family planning (rhythm method) or breast-feeding.
- Fertility awareness.
- Withdrawal.
- Cervical shield.

Pregnancies

To ensure patient safety, each pregnancy in a patient on study treatment must be reported to the Development Innovations Safety Department within 24 hours of learning of its occurrence. The

pregnancy should be followed up for 3 months after the termination of the pregnancy to determine outcome, including spontaneous or voluntary termination, details of the birth, and the presence or absence of any birth defects, congenital abnormalities, or maternal and/or new-born complications.

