Pregnancy should be recorded on a Clinical Study Pregnancy Form and reported by the Investigator to the **Development Innovations Safety Department**. Pregnancy follow-up should be recorded on the same form and should include an assessment of the possible relationship to the study drug of any pregnancy outcome. Any SAE experienced during pregnancy must be reported on the SAE paper report form.

Pregnancy outcomes must be collected for the female partners of any males who took study treatment in this study. Consent to report information regarding these pregnancy outcomes should be obtained from the mother.

Women Not of Childbearing Potential are defined as follows:

- Women are considered post-menopausal and not of childbearing potential if they have had continuous 12 months of natural (spontaneous) amenorrhea with an appropriate clinical profile (e.g., age appropriate, history of vasomotor symptoms).
- Women who are permanently sterilized (e.g., tubal occlusion, hysterectomy, bilateral salpingectomy, bilateral oophorectomy).
- Women who are >45 years-of-age, not using hormone-replacement therapy and who have experienced total cessation of menses for at least 12 months OR who have a follicle stimulating hormone (FSH) value >40 mIU/mL and an estradiol value <40 pg/mL (140 pmol/L).
- Women who are >45 years-of-age, using hormone-replacement therapy and who have experienced total cessation of menses for at least 1 year OR who have had documented evidence of menopause based on FSH >40 mIU/mL and estradiol <40 pg/mL prior to initiation of hormone-replacement therapy.

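### Criterion 8 and Appendix C draw the line for childbearing potential differently for some women, and no text says which definition governs pregnancy testing and contraception

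*Combined protocol and SAP*

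**What the plan says.** Section 3.1, criterion 8, requires a negative serum pregnancy test from WOCBP and refers to Appendix C. Its note also carries a definition. A fertile woman is a WOCBP from menarche "until becoming post-menopausal (no menses for 12 months without an alternative medical cause"), "unless permanently sterile (hysterectomy, bilateral salpingectomy, or bilateral oophorectomy"). Criterion 9 then lists highly effective contraception for WOCBP, and for male patients with WOCBP partners. The accepted methods include "bilateral tubal occlusion, vasectomized partner or sexual abstinence". Criterion 9 also cites Appendix C.

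Appendix C handles the subject in three places:

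- **Opening definition.** WOCBP are "defined as all women physiologically capable of becoming pregnant, must use highly effective contraception during the study".
- **Contraception table, Sterilization row.** This is a method that applies "When a woman of childbearing potential has had surgical bilateral oophorectomy (with or without hysterectomy) or tubal ligation", with a six-week minimum before entry. It adds: "In case of oophorectomy alone, only when the reproductive status of the woman has been confirmed by follow-up hormone level assessment". A separate line below the table accepts bilateral tubal occlusion with no waiting period.
- **Women Not of Childbearing Potential list.** One entry reads "Women who are permanently sterilized (e.g., tubal occlusion, hysterectomy, bilateral salpingectomy, bilateral oophorectomy"). The general menopause entry asks for natural amenorrhea. Two further entries cover women over 45, one without and one with hormone-replacement therapy (HRT). Each is met by 12 months (1 year in the HRT entry) without menses, or alternatively by FSH above 40 mIU/mL with estradiol below 40 pg/mL (measured before HRT began, where relevant). Neither over-45 entry excludes amenorrhea from another medical cause.

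Section 5.2 and the schedule footnotes use the term WOCBP without saying which definition applies.

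**The concern.** WOCBP status decides who has the entry serum test and who must use contraception through the study and for at least 90 days beyond the final dose of a first-in-human drug. Criterion 8 defines that status and then sends the reader to an appendix that contains a fuller list with different boundaries. Two sites could each follow the protocol in good faith and classify the same woman differently.

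Exclusion criterion 18 bars pregnant women regardless of classification. However, Section 5.2 specifies the screening test that would detect a pregnancy only for WOCBP, so the exclusion is not an independent check on a woman classified out of that group.

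**Working it through.** No arithmetic applies. The check applies each text to the same woman and asks what changes.

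| Woman | Criteria 8 and 9 | Appendix C, contraception part | Appendix C, not-of-childbearing-potential list | What differs |
|---|---|---|---|---|
| 1. Tubal occlusion only | WOCBP: the procedure is not among the three that end the status, and criterion 9 names it as contraception | A method for a WOCBP | Not WOCBP | Pregnancy testing only |
| 2. Over 45, FSH/estradiol limits met, under 12 months without menses | No hormone route; menopause requires 12 months | Not addressed beyond the opening definition | Not WOCBP | Testing and contraception, if she counts as fertile under criterion 8 |
| 3. Over 45, 12 months without menses from another medical cause | WOCBP | Not addressed beyond the opening definition | Not WOCBP under the over-45 entries | Testing and contraception |
| 4. Bilateral oophorectomy | Not WOCBP, no condition | A method for a WOCBP: six weeks, plus hormone confirmation if oophorectomy alone | Not WOCBP, no condition | Whether the conditions apply at all |

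**Row 1.** Under either reading the woman already has an accepted highly effective method. Criterion 9 and the line below the Appendix C table both accept tubal occlusion without a waiting period. Only the tests are in question.

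**Row 2.** Criterion 8 offers no hormonal evidence of menopause, while the list joins it to the amenorrhea limb as an alternative. Criterion 8 does begin from the word fertile, and whether a woman with these values is fertile is open to reading. The safe statement is that criterion 8 has no hormone route, not that it certainly makes her a WOCBP.

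**Row 3.** Criterion 8 disqualifies amenorrhea explained by another medical cause. The over-45 entries ask only that menses have stopped. The list's own first entry requires natural amenorrhea, so the list is also uneven within itself. A site applying an over-45 entry as written could omit both the entry test and contraception. The situation is foreseeable: criterion 15 generally requires prior systemic regimens in Part B, and Part B takes patients with breast and cervical cancer.

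**Row 4.** Here the stricter text is the contraception table. Criterion 8 and the list agree with each other, and Appendix C disagrees with itself. The effect is ambiguity about whether hormone confirmation or a six-week interval is expected.

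**Ranking.** Criterion 8 is a mandatory criterion and Appendix C is titled as guidelines, which favours criterion 8. But criteria 8 and 9 both refer to Appendix C, and no sentence says which prevails.

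**The case against.** The best answer is that a governing definition exists. Criterion 8 states outright what a WOCBP is, inside a section that every patient must satisfy, while the appendix is guidance. A site that followed the list for row 3 would also have to pass over Appendix C's own opening rule, that every woman physiologically able to conceive uses contraception. This stands in large part. It makes criterion 8 the natural reading and keeps the severity low. It does not remove the problem, because the protocol sends sites to the appendix and the appendix then gives a different answer.

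Three stronger readings are tempting and are not supported.

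- A reader might infer from the six-week phrase, "tubal ligation at least six weeks prior to study entry", that a recent tubal occlusion leaves a woman without accepted contraception. Criterion 9 and the line below the Appendix C table accept bilateral tubal occlusion with no such condition, so only testing differs.
- A reader might infer that the FSH/estradiol route is unsafe. Nothing in the documents shows hormonal confirmation over age 45 to be inadequate. Whether to accept it is the sponsor's choice; the defect is that the two texts differ.
- A reader might add up the scheduled tests and contraception days that depend on WOCBP status and present the total as the size of the problem. Those totals measure how long a woman stays on treatment, not how many women are misclassified. In Part B, moreover, Table 3 footnote o, read literally, does not confine on-treatment tests to WOCBP. That is a separate drafting matter.

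**Conclusion.** The inconsistency is real and stands in current text. Three groups (rows 1 to 3) fall out of WOCBP status under the Appendix C list without clearly doing so under criterion 8, and bilateral oophorectomy is conditional in one place and unconditional in two others.

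Row 3 matters most, because both the entry test and contraception could be omitted. Row 1 concerns testing only. Row 2 depends on how fertile is read in criterion 8. Row 4 is an ambiguity about extra precautions.

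Severity is low. Any harm requires a site to rely on the list rather than on criterion 8, and the documents give no count of women in any of these groups. Therapy-induced amenorrhea is offered as an example of another medical cause; the documents do not discuss it. Sample size, error rates and the efficacy analysis are unaffected.

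**What to change.** Make the change at the next amendment:

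1. State in criterion 8 and at the head of Appendix C that criterion 8's definition governs pregnancy testing and contraception throughout the protocol.
2. Delete tubal occlusion from the list of women not of childbearing potential. It remains a contraceptive method in criterion 9 and elsewhere in Appendix C.
3. In both over-45 entries, add criterion 8's qualifier to the amenorrhea limb: no other medical cause explains the absence of menses.
4. Have the sponsor decide once, and write identically in criterion 8 and Appendix C, whether the FSH/estradiol route is accepted, and whether bilateral oophorectomy carries a waiting period or hormone confirmation.

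The cost is amendment wording and a few extra pregnancy tests for any woman reclassified as a WOCBP. Urine tests are already allowed on treatment.

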3.2. Exclusion Criteria

Patients who meet any of the following criteria will be excluded from study entry:

1. Clinical laboratory values meeting the following criteria within 4 weeks (28 days) prior to baseline:
 - a. Serum creatinine $\geq 1.5 \times$ upper limit of normal (ULN) AND calculated creatinine clearance ≤ 60 mL/min using Cockcroft-Gault equation.
 - b. Total bilirubin $\geq 1.5 \times$ ULN or $\geq 3.0 \times$ ULN in the presence of documented Gilbert's syndrome.
 - c. Aspartate aminotransferase or ALT $\geq 2.5 \times$ ULN, or AST or ALT $\geq 5.0 \times$ ULN in the presence of liver metastases.
 - d. Hematologic function:
 - i. Absolute neutrophil count (ANC) ≤ 1000 cells/ μ L.

- ii. Hemoglobin \leq 8.5 g/dL or 5.28 mmol/L.
- iii. Platelet count \leq 75,000/ μ L.

2. Significant cardiovascular disease, including:
 - a. Cardiac failure New York Heart Association Class III or IV ([Appendix D](#)), or left ventricular ejection fraction (LVEF) $<$ 50% or below the lower limit of the Institution's normal range.
 - b. Myocardial infarction, severe or unstable angina within 6 months prior to baseline.
 - c. Significant thrombotic or embolic events within 3 months prior to baseline including, but not limited to, stroke or transient ischemic attack. Catheter-related thrombosis and deep vein thrombosis are not a cause for exclusion.
 - d. History or presence of any uncontrolled cardiovascular disease.
 - e. Personal or family history of long QT syndrome.
3. ECG findings obtained using the study site's ECG machine-derived measurements, meeting any of the following criteria:
 - a. Evidence of second- or third-degree atrioventricular block.
 - b. Clinically significant arrhythmia (as determined by the Investigator).
 - c. QTc interval of $>$ 470 msec as calculated according to Fridericia's formula (QTcF = QT/R to R interval^{0.33}).
4. Leptomeningeal or untreated central nervous system (CNS) malignancies (primary or metastatic); patients with asymptomatic CNS metastases who have undergone surgery or radiotherapy 4 weeks prior to C1D1 and who are on a dose of prednisone of no more than 10 mg or equivalent will be eligible for **Part A** of the trial.
5. Received other recent antitumor therapy, including:
 - a. Investigational therapy administered within the 28 days prior to baseline or 5 half-lives, whichever is shorter.
 - b. Any standard chemotherapy, targeted therapy (TKI or mAB), or radiation within 14 days prior to baseline.
 - c. Any antineoplastic mAbs within 21 days or checkpoint immunotherapy (including, but not limited to, pembrolizumab, nivolumab, atezolizumab, or durvalumab) within 3 months prior to baseline.
6. Taking or unable to discontinue proton pump inhibitors within 1 week prior to baseline.
7. Known concurrent [REDACTED] mutation.
8. Known tumor-harboring resistance mutations including [REDACTED] or [REDACTED] mutations or [REDACTED] mutations.
9. Prior documented treatment response (i.e., complete response [CR], partial response [PR], or stable disease [SD] lasting \geq 24 weeks by Response Evaluation Criteria in Solid

Tumors [RECIST] v1.1) to approved or investigational [REDACTED] or [REDACTED] therapies (e.g., afatinib, lapatinib, dacomitinib, neratinib, trastuzumab deruxtecan, poziotinib, mobocertinib, amivantamab).

- Patients with or without tumor response discontinuing after 8 weeks or less of therapy due to toxicity may be considered after discussion with the Sponsor Medical Monitor.
- Patients with an NGS test (tissue or plasma) obtained within 8 weeks of Baseline which does not include any mutations listed in Exclusion Criteria 7 or 8 may be considered after discussion with the Sponsor Medical Monitor.

10. Major surgery within 4 weeks before baseline or scheduled for surgery during projected course of the study.
11. Received a transfusion of whole blood or red blood cells within 1 week, or platelet transfusion within 2 weeks before baseline.
12. Any history of concomitant condition (e.g., alcohol abuse or psychiatric condition) that, in the opinion of the Investigator, would compromise the patient's ability to comply with the study or interfere with the evaluation of the safety and efficacy of the study drug.
13. Known concurrent malignancy that is expected to require active treatment within 2 years and that may interfere with the interpretation of the efficacy and safety outcomes of the study in the opinion of the treating Investigator confirmed by the Medical Monitor. Prior malignancy that is at a low risk of progression or recurrence (e.g., superficial bladder cancer, non-melanoma skin cancers, or low-grade prostate cancer not requiring therapy) is allowed.
14. Known active hepatitis B or C infection and/or known human immunodeficiency virus (HIV) carrier.
15. Any history (within 6 months) or presence of poorly controlled gastrointestinal disorders that may interfere with absorption of the study drug including delayed gastric emptying, chronic diarrhea associated with intestinal malabsorption, ulcerative colitis or Crohn's disease that requires steroid therapy at any dose, refractory nausea and vomiting, and/or prior surgical procedures affecting absorption or requirement of intravenous alimentation.
16. Taking medications or herbal supplements that are known potent CYP3A4 inhibitors/inducers (including St. John's wort, kava, ephedra [ma huang], ginkgo biloba, dehydroepiandrosterone [DHEA], yohimbe, saw palmetto, ginseng, and double-strength grapefruit juice) within 14 days before the start of treatment through permanent discontinuation of study treatment (See [Appendix E](#)).
17. Taking medications that are known to have a risk to cause QT interval and/or Torsades de pointes within 14 days before the start of treatment through permanent discontinuation of study treatment ([Appendix F](#)).
18. Women who are pregnant or breast-feeding.

